#### **10.2.** Risk Minimization

Refer to "Prevention and Mitigation" column in the table under Section 10.1.

#### **10.3.** Potential Benefits

Subjects are not expected to benefit from participation in this study; however, they may gain increased awareness of emerging technologies for diabetes management as a result of their participation.

#### 10.4. Risk-Benefit Rationale

The main benefit of this study is that patients may experience improved glucose control. The risk, as with all automated systems, is the possibility of an increase in hypoglycemia. To address this risk, many scenarios have been modeled and the risk is effectively minimized by a variety of safety checks that are an integral part of the revised device algorithm.

#### **10.5.** Risk Determination

In the opinion of the sponsor, this study is considered to be a significant risk (SR) study. Results of an evaluation of the requirements per 21 CFR Part 812.3, led to the SR determination as follows:

- The devices could present a potential for serious risk to subject health, safety or welfare.
- The devices are for a use of substantial importance in treating disease, and presents potential for serious risk to subject health, safety or welfare.

Therefore, submission of an Investigational Device Exemption (IDE) application to the United States Food and Drug Administration is required.

10813115DOC

Version D

#### **11. Adverse Events Assessments**

#### **11.1. Adverse Events**

Throughout the course of the study, investigational centers will make all efforts to remain alert to possible reportable adverse events (AEs) or untoward findings. The study personnel will elicit reports of AEs from the subject at each visit (including phone calls) starting at the time of signing the informed consent documenting the medical diagnosis, date of event start and end, causality (relationship to device or procedure), treatment, outcome, and description that includes the details of the event.

#### 11.2. Definitions and Classification of Adverse Events

Medtronic uses the definitions provided in ISO 14155:2020 and 21 CFR 812 for AE definitions. Where the definition indicates "device", it refers to any device used in the study. This might be the device under investigation, or any market released component of the system.

**Severe Hypoglycemia** is an event requiring assistance of another person due to altered consciousness to actively administer carbohydrate, glucagon, or other resuscitative actions. This means that the subject was impaired cognitively to the point that he/she was unable to treat himself or herself, was unable to verbalize his or her needs, and was incoherent, disoriented and/or combative.

These episodes may be associated with sufficient neuroglycopenia to induce seizure or coma. Plasma glucose measurements may not be available during such an event, but neurological recovery attributable to the restoration of plasma glucose to normal is considered sufficient evidence that the event was induced by a low plasma glucose concentration. **(Adapted from American Diabetes Association Workgroup on Hypoglycemia, Diabetes Care 28:1245-1249, 2005)** 

**Severe Hyperglycemia** is defined as hyperglycemia (blood glucose greater than (>) 300 mg/dL or 16.7 mmol/L) with blood glucose ketones greater than (>) 1.5 mmol/L, urine ketones moderate or large, or accompanied by symptoms of nausea, vomiting or abdominal pain.

**Diabetic Ketoacidosis/DKA diagnostic criteria**: blood glucose greater than (>) 250 mg/dL or greater than (>) 13.9 mmol/L, arterial pH less than (<) 7.3, bicarbonate less than (<) 15 mEq/L, moderate ketonuria or ketonemia and requiring treatment within a health care facility. (American Diabetes Association-Diabetes Care, Volume 27, Supplement 1, January 2004; S94-S102)

Hyperglycemic events will be recorded as DKA if the event includes the presence of all of the following:

- Arterial blood pH less than (<) 7.30 or serum bicarbonate less than (<) 15 mEq/L
- Blood glucose greater than (>) 250 mg/dL or greater than (>) 13.9 mmol/L
- Serum ketones or large/moderate urine ketones
- Symptoms such as polyuria, polydipsia, nausea, or vomiting
- Treatment provided in a health care facility

Page 78 of 118

#### Adverse Event (AE) (ISO 14155:2020)

10813115DOC

Any untoward medical occurrence, unintended disease or injury, or untoward clinical signs (including abnormal laboratory findings) in subjects, users or other persons, whether or not related to the investigational medical device and whether anticipated or unanticipated.

**Note 1 to entry:** This definition includes events related to the investigational medical device or the comparator.

**Note 2 to entry:** This definition includes events related to the procedures involved.

Version D

**Note 3 to entry:** For users or other persons, this definition is restricted to events related to the use of investigational medical devices or comparators.

#### Adverse Device Effect (ADE) (ISO 14155:2020)

Adverse event related to the use of an investigational medical device.

- **Note 1 to entry**: This definition includes adverse events resulting from insufficient or inadequate instructions for use, deployment, implantation, installation, or operation, or any malfunction of the investigational medical device.
- **Note 2 to entry**: This definition includes any event resulting from use error or from intentional misuse of the investigational medical device.
- **Note 3 to entry:** This includes 'comparator' if the comparator is a medical device.

#### Serious Adverse Event (SAE) (ISO 14155:2020)

Adverse event that led to any of the following

- a) death,
- b) serious deterioration in the health of the subject, users, or other persons as defined by one or more of the following:
  - 1. a life- threatening illness or injury, or
  - 2. a permanent impairment of a body structure or a body function including chronic diseases, or
  - 3. in-patient\* or prolonged hospitalization, or
  - 4. medical or surgical intervention to prevent life-threatening illness or injury or permanent impairment to a body structure or a body function,
- c) foetal distress, foetal death or a congenital abnormality or birth defect including physical or mental impairment

**Note 1 to entry**: Planned hospitalization for a pre-existing condition, or a procedure required by the CIP, without serious deterioration in health, is not considered a serious adverse event.

## CIP321 Clinical Investigation PlanPage 79 of 118Medtronic10813115DOCVersion DPage 79 of 118Medtronic

\* For the purpose of this study, Inpatient Hospitalization is defined as: admission to the hospital for a period of 24 hours or more based on urgent medical need rather than elective admission.

For the purpose of this study, the term "life-threatening" in the definition of "serious" refers to an event in which the patient was at risk of death at the time of the event; it does not refer to an event which hypothetically might have caused death if it were more severe. (ICH Topic E 2 A Clinical Safety Data Management: Definitions & Standards for Expedited Reporting. EMEA 2006)

#### Serious Adverse Device Effect (SADE) (ISO 14155:2020)

Adverse device effect that has resulted in any of the consequences characteristic of a serious adverse event

#### Unanticipated Adverse Device Effect (UADE) (21 CFR 812.3(s))

Any serious adverse effect on health or safety or any life-threatening problem or death caused by, or associated with, a device, if that effect, problem, or death was not previously identified in nature, severity, or degree of incidence in the investigational plan or application (including a supplementary plan or application), or any other unanticipated serious problem associated with a device that relates to the rights, safety, or welfare of subjects.

#### **11.3. Reporting of Adverse Events**

The investigator or designee will record ALL AEs while the subject is enrolled in the clinical study.

Each AE needs to be assessed for its device or procedure relatedness. A device related AE is associated with the use of the study device (e.g. infection of sensor site or infusion set occlusion resulting in DKA). A procedure related AE is associated with testing related to the study procedures specified in the CIP (e.g. IV insertion pain).

Examples of device or procedure related AEs include:

- *Device* related (ADE): insertion site infection
- Serious adverse *device effect*: cellulitis at device insertion site requiring hospitalization
- *Procedure* related AE: bruising at IV insertion site

Subjects participating in the study have diabetes and are expected to experience hypoglycemia and or hyperglycemia. These normal events are not expected to be reported to sponsor as this is not considered an untoward event, but rather an expected occurrence. Any glycemic excursion that meets the protocol definition of Severe Hypoglycemia, Severe Hyperglycemia or DKA is considered an untoward event and a worsening from the subject's baseline and would be reported to sponsor on an AE eCRF.

Baseline medical conditions should only be reported to sponsor on an AE eCRF if there is a worsening from the subject's baseline. For example, a subject previously diagnosed with Asthma is hospitalized for severe asthma attack would be a reportable event.

Adverse events will be documented in the subject source file and reported to sponsor on an eCRF. The investigational center is responsible for documentation of AEs including obtaining source documents related to the event, such as emergency medical technician/paramedic reports, hospital records (admission summary; lab results, test results, discharge summary) or device uploads to support the event. Source documents will be reviewed to determine if additional AEs have occurred and require reporting.

CIP321 Clinical Investigation Plan				
10813115DOC	Version D	Page 80 of 118		Medtronic

Adverse events that have not resolved at the time of the subject's discontinuation or completion of the study should have an "outcome" of Not Recovered/Not Resolved at study end in subject source and on an eCRF. The investigator should ensure that subject is aware of any follow-up or additional treatment that is required for any ongoing AE at end of study participation; however, there will be no eCRF entry for the ongoing follow-up.

#### **11.4. Notification of Adverse Events**

#### Sponsor Notification:

The investigational center staff must report all reportable AEs to Medtronic in a timely manner. All Severe Hypoglycemia, DKA, SAE, and SADE should be reported as soon as possible (desired within 24 hours of investigator or study coordinator awareness) to Medtronic. For the previously mentioned events, the AE eCRF will be completed with all known details as soon as possible, this will serve as notification to Medtronic. If the study database cannot be accessed due to technical problems, contact the sponsor via email at [contact] and provide the known details of the event. Once the access issue has been corrected, the event should be entered onto an AE eCRF.

Source documents that support the event (e.g. clinic notes, hospital admission and discharge records, lab reports, EMT reports, ER/Urgent Care) should be provided to the sponsor via the Medtronic BOX safety folder. All source documents/medical records should be redacted of patient identifiers (full name, address, etc.) prior to providing to the sponsor. Each source page should be identified with the subject ID.

#### **11.5. Expedited Safety Reporting Requirements**

For device studies, investigators are required to submit a report of a UADE to the sponsor and the reviewing IRB as soon as possible, but in no event later than 10 working days after the investigator first learns of the event (812.150(a)(1)).

The sponsor will notify the investigator and IRB of any event that results in a safety report per regulations to the FDA. Documentation of IRB notification of any safety event must be kept at the investigational center and a copy sent to the sponsor.

It is the responsibility of the investigator to follow their IRB reporting requirements.

#### **11.6.** Causality Assessment

An AE is not automatically related to the study device or procedure simply because the subject is wearing the device and participating in the study. The event should be reviewed to determine if the device or study procedure could have possibly caused the event and therefore is related to the study device or procedure.

Causality assessment is the determination of the relationship between an AE and the device being studied. It is expected that the investigational center will review all elements surrounding the AE to properly assess the causality of the event to the study device or to a study procedure.

This review would include the subjects' description of the event, study device uploads and medical records (if applicable) from the treating facility. These records will be made available to sponsor.

Investigators should classify the relationship between the AE and the study device or study procedures

10813115DOC Version D Page 81 of 1	.18	Medtronic

using one of the five possible causality categories listed below:

- **Not related:** relationship to the device or procedures can be excluded when:
  - the event is not a known side effect of the product category the device belongs to or of similar devices and procedures
  - the event has no temporal relationship with the use of the investigational device or the procedures;
  - the event does not follow a known response pattern to the medical device (if the response pattern is previously known) and is biologically implausible;
  - the discontinuation of medical device application or the reduction of the level of activation/exposure - when clinically feasible – and reintroduction of its use (or increase of the level of activation/exposure), do not impact on the serious event;
  - the event involves a body-site or an organ not expected to be affected by the device or procedure;
  - the event can be attributed to another cause (e.g. an underlying or concurrent illness/ clinical condition, an effect of another device, drug, treatment or other risk factors);
  - the event does not depend on a false result given by the investigational device used for diagnosis, when applicable;
  - harms to the subject are not clearly due to use error;
  - In order to establish the non-relatedness, not all the criteria listed above might be met at the same time, depending on the type of device/procedures and the serious event.
- **Unlikely:** the relationship with the use of the device seems not relevant and/or the event can be reasonably explained by another cause, but a relationship to the device cannot be completely ruled out.
- **Possible:** the relationship with the use of the investigational device is weak. Alternative causes are also possible (e.g. an underlying or concurrent illness/ clinical condition or/and an effect of another device, drug or treatment). Cases where relatedness cannot be assessed should also be classified as possible.
- **Probable:** the relationship with the use of the investigational device seems relevant and/or the event cannot reasonably be explained by another cause.
- **Causal relationship:** the event is associated with the investigational device or with procedures beyond reasonable doubt when:
  - the event is a known side effect of the product category the device belongs to or of similar devices and procedures;
  - the event has a temporal relationship with investigational device use/application or procedures;
  - the event involves a body-site or organ that
    - the investigational device or procedures are applied to;
    - the investigational device or procedures have an effect on;
  - the event follows a known response pattern to the medical device (if the response pattern is previously known);
  - the discontinuation of medical device application (or reduction of the level of activation/exposure) and reintroduction of its use (or increase of the level of activation/exposure), impact on the event (when clinically feasible);

## CIP321 Clinical Investigation Plan Page 82 of 118 Medtronic 10813115DOC Version D Page 82 of 118 Medtronic

- other possible causes (e.g. an underlying or concurrent illness/ clinical condition or/and an effect of another device, drug or treatment) have been adequately ruled out;
- harm to the subject is due to error in use;
- the event depends on a false result given by the investigational device used for diagnosis, when applicable;
- In order to establish the relatedness, not all the criteria listed above might be met at the same time, depending on the type of device/procedures and the serious event.

Example: A severe hyperglycemia AE with the following event description would have the following causality assessment for device relatedness:		
Improved glucose without an infusion set/site change Not related		
Changed infusion set with glucose improvement	Possible	
Infusion set fell out, bent cannula, occlusion alarm	Causal relationship	

#### 11.7. Anticipated or Unanticipated

If an AE is determined to be related to the study device, the sponsor will then assess the event to determine if it is anticipated or unanticipated.

- **Anticipated:** the event is identified in the CIP; labeling; report of priors/ Investigator's Brochure (IB) or user guide.
- Unanticipated: the event has not been previously identified in the CIP; labeling; report of priors/IB or user guide.

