# 9.12.2. Stopping Rules for Entire Study

During the study period, the following steps will be taken for:

- Unanticipated Adverse Device Effects (UADE) •
- Device related Diabetic Ketoacidosis (DKA) •
- Device related Severe hypoglycemia •
- 1. Site will notify the sponsor within approximately 24 hours of receiving knowledge of the event.
- 2. Sponsor will notify Food and Drug Administration (FDA) within approximately 72 hours of knowledge of the event and provide updates to those agencies as information becomes available.
- 3. Clinical Events Committee (CEC) is to review the event within 7 days from the time that the sponsor is notified.
- 4. CEC will provide recommendation to the sponsor on the following:
  - a) If enrollment and study may continue
  - b) If enrollment should be stopped; enrolled subjects are still allowed to continue in study
  - c) If the entire study must be stopped, including subjects who have already received study devices.

Page 69 of 118

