Risks with the use of an insulin infusion pump may include the risk of malfunction of the components of the system (pump, software, infusion set and reservoir) as well as the risk of use error during use of the system. Device deficiencies or use errors can result in administration of too much or too little insulin which can lead to the following clinical consequences: 
 
Hypoglycemia
 
Hyperglycemia
 
Diabetic ketoacidosis
 
Severe hypoglycemia with or without associated seizure, coma or death
 
Kinked cannula leading to hyperglycemia
 
Infusion set disconnection from pump leading to hyperglycemia
 
Subject removes the reservoir from the pump but forgets to disconnect the infusion
 
	
 
Prevention and mitigation include:
 
Follow the provided user guides & instructions for insulin pump management which includes information on infusion set change.
 
Train prior to study device use on appropriate device use and diabetes management principles and instruct to call investigator with problems.
 
Instruct to check their meter glucose if their high or low symptoms do not match their sensor alerts or sensor glucose readings in order to make diabetes treatment decisions.
 
Instruct to check their meter glucose if there are any concerns that the sensor glucose value is not accurate.
 
Instruct to change infusion set if suspected catheter occlusion or administer insulin with syringe for persistent hyperglycemia especially if
 

This document is electronically controlled *Medtronic Business Restricted* 056-F275, vB Clinical Investigation Plan Template

10813115DOC Ve	rsion D	Page 71 of 118		Medtronic

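### Section 11.7 sorts device-related events into anticipated and unanticipated without the severity and incidence tests in the plan's own UADE definition, so the sponsor's classification could miss a UADE

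*Protocol*

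**What the plan says.** Under Protocol Section 11.7, once an adverse event is judged device related, "the sponsor will then assess the event to determine if it is anticipated or unanticipated". It is anticipated if "the event is identified in the CIP; labeling; report of priors/ Investigator's Brochure (IB) or user guide", and unanticipated if "the event has not been previously identified in the CIP; labeling; report of priors/IB or user guide".

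The UADE definition in Section 11.2, taken from 21 CFR 812.3(s), covers a serious device effect "if that effect, problem, or death was not previously identified in nature, severity, or degree of incidence in the investigational plan or application". It also covers "any other unanticipated serious problem associated with a device that relates to the rights, safety, or welfare of subjects".

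The UADE class is used in three places:

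- It is a safety endpoint (Protocol 4.2.3 and 14.4.3; SAP 4.2.3, 7.2.3 and 7.10).
- It obliges the investigator to report within 10 working days (Protocol 11.5).
- It is the first of three triggers in Protocol 9.12.2. The other two are device-related DKA and device-related severe hypoglycemia. Each trigger starts site notice to the sponsor in about 24 hours, sponsor notice to FDA in about 72 hours, Clinical Events Committee (CEC) review within 7 days, and a CEC recommendation on continuing.

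Table 3 in Protocol 10.1 lists the potential risks. One entry is "Severe hypoglycemia with or without associated seizure, coma or death". Others include cardiovascular event, shock, coma, infection and allergic reaction.

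**The concern.** Section 11.7 is the only step in the plan that tells the sponsor how to decide whether a device-related event was anticipated. It asks one question: has the event been named? It does not ask whether the case was worse than the one named, or whether such cases are more frequent than expected, and it does not refer back to 11.2.

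The Section 11.2 definition does ask those questions. A known harm that appears in a graver form, or at an unexpected rate, is what its severity and incidence criteria are there to catch. If the sponsor relies on 11.7 alone, such an event is labelled anticipated and may be left out of the UADE count. For some harms it would also not enter the 9.12.2 review.

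**Working it through.** No arithmetic applies, because the point rests on no sample size, power or event figure. The check sets the two rules side by side and follows the UADE label to where it is used.

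**Step 1: the two tests.**

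| Feature | UADE definition, 11.2 | Classification rule, 11.7 |
|---|---|---|
| Events covered | Serious device effects | Any device-related event |
| New kind of effect | Yes | Yes (event not named) |
| Worse than described | Yes | Not mentioned |
| More frequent than described | Yes | Not mentioned |
| Other serious problems | Yes | Not mentioned |
| Compared with | Investigational plan or application | CIP, labeling, report of priors or IB, user guide |

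The definition gives three ways to be unanticipated plus a residual category; 11.7 gives one. The residual category does not clearly rescue the position. It depends on the word unanticipated, and the only place the plan explains that word is 11.7.

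**Step 2: what counts as named.** Table 3 often lists a harm with no severity limit: infection and allergic reaction under sensors, cardiovascular event and shock under hyperglycemia. The severe hypoglycemia entry extends to death. Many entries carry no expected frequency. Outside the reference rates in Table 4, which cover only severe hyperglycemia, DKA and severe hypoglycemia, there is little against which an excess incidence could be judged. Read literally, 11.7 makes these harms anticipated once they appear in the list.

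**Step 3: consequence by type of event.**

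- *Device-related DKA and severe hypoglycemia.* Each has its own trigger in 9.12.2, whatever its label. Only the UADE count and UADE reporting are exposed.
- *Other listed serious device effects.* Examples are a serious site infection, a severe allergic reaction, a cardiovascular event, or a serious hyperglycemic event short of DKA. UADE is their only trigger in 9.12.2. Section 12.1 asks the CEC to weigh severe hyperglycemia in its recommendation to the sponsor, yet 9.12.2 gives that event no trigger of its own.

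**Step 4: the endpoint.** SAP 7.10 lists UADEs among the events to be summarized but does not define them or say whether 11.2 or 11.7 governs the count.

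**The case against.** A reader might infer that a harm in Table 3 can never be a UADE, or that the UADE count for such harms is zero by construction. The documents do not support this:

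- The 11.2 definition stands. The same section says the plan uses the 21 CFR 812 definitions. Section 11.7 does not use the term UADE and does not claim to replace the definition.
- The investigator's report in 11.5 does not depend on the sponsor's label in 11.7.
- Section 12.1 lets the CEC consider whether a device-related event was unanticipated.
- Naming a harm does not always cover every grade. Table 3 lists localized infection for infusion sets, so a systemic infection from that source is arguably not identified even under 11.7.

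Nor would a severe hypoglycemia rate well above the Table 4 references go unexamined. Each device-related case starts the 9.12.2 steps, and Section 12.2 tells the Data Monitoring Committee (DMC) to consider stopping if rates are significantly worse than the trial rates in Table 4.

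Other listed serious harms have cover too. SAEs and SADEs should reach the sponsor as soon as possible, desirably within 24 hours (11.4). The CEC reviews all SAEs, SADEs and severe hyperglycemia events (12.1). The DMC tracks rates of SAEs and device-related events, may meet ad hoc and may recommend halting (12.2). SADE is its own endpoint, so a serious listed harm is still counted.

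All of this stands, and it limits the point. It does not remove it. The plan still holds two tests that disagree, and the one written as the sponsor's step is the narrower. CEC consideration of anticipation is optional, and 12.1 refers to 9.12.2 for the 7-day requirement. Scheduled DMC meetings are about 90 days apart, roughly the length of the study period, and DMC review does not make an event a UADE.

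**Conclusion.** The inconsistency is real. Section 11.7 is narrower than the plan's UADE definition, and the sponsor's classification could miss an event that qualifies on severity or incidence. That is as far as the texts go: a possible misclassification, not a closed route.

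The effect cannot be put as a number. For DKA and severe hypoglycemia it is confined to UADE labelling and counting. For other listed serious device effects, a missed label also loses the 24-hour, 72-hour and 7-day steps of 9.12.2 and the CEC recommendation attached to them, leaving the partial cover described above.

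This rests on two assumptions: that the sponsor applies 11.7 as written without returning to 11.2, and that no separate sponsor procedure supplies the missing tests. The labeling, brochure and user guides are not in the documents, so how far they describe severity or frequency is unknown. The correction is worth making because it concerns safety classification and costs little.

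**What to change.** Reconcile Protocol 11.7 with 11.2. State in 11.7 that a serious device-related event is unanticipated if it was "not previously identified in nature, severity, or degree of incidence in the investigational plan or application", or if it is "any other unanticipated serious problem associated with a device that relates to the rights, safety, or welfare of subjects", and cite the 11.2 UADE definition as governing. The cross-reference also settles which source documents count, since the two sections list different ones. In SAP 7.10, state that UADEs are counted on the 11.2 definition.

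The change should not make Table 4 the formal incidence standard. Its severe hyperglycemia entries are NA for ages 15 and over. Its severe hypoglycemia references run from 0 to 20.9 per 100 patient-years with none chosen. DMC meetings about every 90 days also do not fit a 10-working-day report.

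The cost is a short text change in each document and occasional extra UADE assessments and reports. No dose, treatment rule or stopping threshold changes.
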